5.4 Patient enrollment

All patients will be centrally assigned to study drug using an interactive voice/web response system (IVRS/IWRS). Before the study is initiated, the telephone number and call-in directions for the IVRS and/or the log-in information and directions for the IWRS will be provided to each site.

Investigators should keep a record (ie, the patient screening log) of patients who entered screening.

At screening/baseline (Days -28 to -1), the Investigators or suitably trained delegate will:

- Obtain signed informed consent before any study specific procedures are performed. If laboratory or imaging procedures were performed for alternate reasons prior to signing

consent, these can be used for screening purposes with consent of the patient. However, all screening laboratory and imaging results must have been obtained within 28 days of the first dose, with the exception of PFTs, which must have been obtained within 8 weeks of study enrollment.

- Obtain a unique 7-digit enrollment number (E-code), through the IVRS/IWRS in the following format (ECCNNXXX: CC being the country code, NN being the center number, and XXX being the patient enrollment code at the center). This number is the patient's unique identifier and is used to identify the patient on the electronic case report forms (eCRFs).
- Determine patient eligibility (see Sections [5.1](#) and [5.2](#)).
- Obtain signed informed consent for genetic research study (optional).

Patients will begin treatment on Day 1. Patients must not be treated unless all eligibility criteria have been met.

If a patient withdraws from participation in the study, then his or her enrollment code cannot be reused. Withdrawn patients will not be replaced.

5.5 Procedures for handling incorrectly enrolled patients

Patients who fail to meet the eligibility criteria should not, under any circumstances, be enrolled or receive study medication. There can be no exceptions to this rule. Patients who are enrolled, but subsequently found not to meet all the eligibility criteria must not be initiated on treatment, and must be withdrawn from the study.

Where a patient does not meet all the eligibility criteria but is incorrectly started on treatment, the Investigator should inform the AstraZeneca Study Physician immediately, and a discussion should occur between the AstraZeneca Study Physician and the Investigator regarding whether to continue or discontinue the patient from treatment. The AstraZeneca Study Physician must ensure all decisions are appropriately documented and that the potential benefit:risk profile remains positive for the patient.

5.6 Screen failures

Screen failures are patients who do not fulfill the eligibility criteria for the study, and therefore must not be dosed. These patients should have the reason for study withdrawal recorded as "screen failure" (ie, patient does not meet the required inclusion/exclusion criteria). This reason for study withdrawal is only valid for screen failures (ie, not dosed patients). Patients may be rescreened a single time, but they may not be re-assigned IP treatment. If a patient who has failed screening is rescreened, a new E-code must be assigned. Patients will reconfirm their consent to participate in the study by re-signing and dating their original consent form(s), next to their initial signature and date.

A minimal set of screen failure information is required to ensure transparent reporting of screen failure patients to meet the Consolidated Standards of Reporting Trials publishing requirements and to respond to queries from regulatory authorities. Minimal information includes demography, screen failure details, eligibility criteria, and any AEs/SAEs.

6 STUDY TREATMENTS AND CONCOMITANT THERAPY

Study treatments are all pre-specified, IPs and NIPs, medical devices and other interventions (eg, surgical and behavioral) intended to be administered to the study patients during the study conduct. Study treatment in this study refers to durvalumab monotherapy.

6.1 Treatments administered

AstraZeneca will supply durvalumab. Details of study treatment are described in [Table 5](#). Dose modifications are described in [Section 6.5](#).

Table 5 Study Treatment

	Durvalumab
Study treatment name:	Durvalumab
Type:	Biologic
Dosage formulation: ^a	500-mg vial solution for infusion after dilution, 50 mg/mL
Unit dose strength:	500 mg (50 mg/mL)
Route of administration:	IV infusion
Use:	Experimental
IP and NIP:	IP
DosageRegimen: ^b	1500 mg; 20 mg/kg in patients who weigh \leq 30 kg; q4w ^c
Packaging and labeling:	Study treatment will be provided in 500 mg vials. Each vial will be labeled in accordance with GMP Annex 13 and per country regulatory requirement. ^d
Sourcing:	AstraZeneca

GMP = Good Manufacturing Practice; IP – investigational product; IV = Intravenous; NIP = non-investigational product; q4w = Every 4 weeks.

Note: Cycles of durvalumab are 28 days.

^a Refer to [Section 6.1.1.1](#) for detailed formulation and preparation instructions for durvalumab.

^b Detailed instructions for durvalumab administration are provided below. Refer to [Section 6.1.1.1](#) for details on duration of treatment.

^c If a patient's weight falls to 30 kg or below, the patient should receive weight-based dosing equivalent to 20 mg/kg of durvalumab q4w until the weight improves to $>$ 30 kg, at which point the patient should start receiving the fixed-dosing of durvalumab 1500 mg q4w.

^d Label text prepared for durvalumab will show the product name as "MEDI4736" or "durvalumab" depending upon the agreed product name used in the approved study master label document. All naming conventions are correct during this transitional period.

6.1.1.1 Durvalumab

Durvalumab will be supplied by AstraZeneca as a 500-mg vial solution for infusion after dilution. The solution contains 50 mg/mL durvalumab, 26 mM histidine/histidine-hydrochloride, 275 mM trehalose dihydrate, and 0.02% weight/volume (w/v) polysorbate 80; it has a pH of 6.0 and density of 1.054 g/mL. The label-claim volume is 10.0 mL. Investigational product vials are stored at 2°C to 8°C (36°F to 46°F) and must not be frozen. Investigational product should be kept in original packaging until use to prevent prolonged light exposure.

Preparation of durvalumab doses for administration with an IV bag

The dose of durvalumab for administration must be prepared by the Investigator's or site's designated durvalumab manager using aseptic technique and following local practices and site requirements. Total time from needle puncture of the durvalumab vial to the start of administration should not exceed:

- 24 hours at 2°C to 8°C (36°F to 46°F)
- 4 hours at room temperature

A dose of 1500 mg (for patients > 30 kg in weight) will be administered using an IV bag containing 0.9% sodium chloride for injection or 5% dextrose, with a final durvalumab concentration ranging from 1 to 15 mg/mL, and delivered through an IV administration set with a 0.2- or 0.22- μ m filter. Add 30.0 mL (ie, 1500 mg) of durvalumab to the IV bag. The IV bag size should be selected such that the final concentration is within 1 to 15 mg/mL. Mix the bag by gently inverting to ensure homogeneity of the dose in the bag.

If patient weight falls to \leq 30 kg, weight-based dosing at 20 mg/kg will be administered using an IV bag containing 0.9% sodium chloride for injection or 5% dextrose, with a final durvalumab concentration ranging from 1 to 15 mg/mL, and delivered through an IV administration set with a 0.2- or 0.22- μ m filter.

The use of elastometric pumps and use of a pneumatic tube for transport of either a vial or a final prepared product have not been studied; please contact AstraZeneca before using.

Do not co-administer other drugs through the same infusion line.

The IV line will be flushed with a volume of IV diluent equal to the priming volume of the infusion set used after the contents of the IV bag are fully administered, or complete the infusion according to institutional policy to ensure the full dose is administered. Infusion time does not include the final flush time.

If the final product is stored at both refrigerated and ambient temperatures, the total time must not exceed 24 hours otherwise a new dose must be prepared from new vials. Durvalumab does not contain preservatives, and any unused portion must be discarded immediately after use.

6.1.2 Dose and treatment regimens

6.1.2.1 Durvalumab monotherapy

All patients will receive 1500 mg durvalumab via IV infusion q4w for 12 months (13 doses/cycles), starting on Week 0. The last administration of durvalumab will be on week 48 unless there is clinical progression, RECIST 1.1-defined radiological progression, unacceptable toxicity, withdrawal of consent, or another discontinuation criterion is met. See [Figure 2](#). (Please note, if a patient's weight falls to 30 kg or below, the patient should receive weight-based dosing equivalent to 20 mg/kg of durvalumab q4w after consultation between Investigator and Study Physician, until the weight improves to > 30 kg, at which point the patient should start receiving the fixed-dosing of durvalumab 1500 mg q4w).

The durvalumab infusion time is 1 hour \pm 10 minutes; however, if there are interruptions, the total allowed time must not exceed 8 hours with the infusion back maintained at room temperature, otherwise a new dose must be prepared from new vials.

Figure 2 Durvalumab monotherapy dosing schedule

		Durvalumab 1500 mg dose q4w					
Cycle	Week	↓	↓	↓	↓	↓	↓
		1	2	3	4	5 to 13 or PD ^a (12 months)	
		0-3	4-7	8-11	12-15	q4w \pm 3 days until 48 weeks	

PD = Progression of disease; q4w = Every 4 weeks.

^a Or until discontinuation of study drug due to any of the reasons listed in Section [7.1](#).

6.1.3 Duration of treatment and criteria for treatment through progression

Treatment will be administered beginning on Day 1 for 12 months for durvalumab monotherapy or until clinical progression or RECIST 1.1-defined radiological progression (refer to [Appendix F](#)) unless there is unacceptable toxicity, withdrawal of consent, or another discontinuation criterion is met.

During the treatment period, patients who are clinically stable at an initial RECIST 1.1-defined PD may continue to receive study treatment at the discretion of the Investigator and patient as long as they are deemed to be receiving clinical benefit. A follow-up scan is to be collected after the initial RECIST 1.1-defined PD, 4-8 weeks after the prior assessment of PD; this follow-up scan is evaluated using the post-progression evaluation criteria outlined in [Appendix F](#). Patients with confirmed PD who continue to receive durvalumab at the discretion of the Investigator and patient (following consultation with AstraZeneca) can receive treatment for the remainder of the 12-month treatment period, and image acquisitions and tumor assessments should continue on their regular imaging schedule for the duration of treatment.

Patients with rapid tumor progression or with symptomatic progression that requires urgent medical intervention (eg, central nervous system metastasis, respiratory failure due to tumor compression, or spinal cord compression) will not be eligible for continuing durvalumab.

For all patients who are treated through progression, the Investigator should ensure that:

- The patient does not have any significant, unacceptable, or irreversible toxicities that indicate continuing treatment will not further benefit the patient. The patient must not have experienced a toxicity that required permanent discontinuation of study treatment.
- There is absence of clinical symptoms or signs indicating clinically significant disease progression accompanied by a decline in WHO/ECOG PS to > 2.
- There is absence of rapid disease progression or threat to vital organs or critical anatomical sites (eg, central nervous system metastasis, respiratory failure due to tumor compression, or spinal cord compression) requiring urgent alternative medical intervention.
- The patient still fulfills the eligibility criteria for this study (see Section 5.1 and 5.2) with the exception of inclusion criteria 9, 11, and 14 and exclusion criterion 17.
- Patient agrees to re-consenting to be treated through progression.

Patients will not be permitted to continue treatment with durvalumab if progression occurs after confirmed response (CR or PR as defined by RECIST 1.1) in the TLs (regardless of the appearance of new lesions) (ie, the response and progression events both occurred in the TL while receiving durvalumab).

Patients who AstraZeneca and the Investigator determine may not continue treatment after RECIST 1.1-defined PD will be followed up for survival. Patients who have discontinued treatment due to toxicity or symptomatic deterioration, or who have commenced subsequent anticancer therapy, will be followed up with tumor assessments until RECIST 1.1-defined PD plus an additional follow-up scan or until death (whichever comes first) and followed for survival (refer to Section 7.1.2).

Treatment after final overall survival data cutoff

At the time of the DCO, the analysis portion of the clinical study will have been completed and all patients remaining in the study will be considered to have completed the analysis portion of the study. At the time of DCO, the clinical study database will be closed to new data.

Patients in OS follow-up (progressed and have discontinued treatment) will be considered to have completed the study.

Patients who are receiving treatment at the time of DCO may continue receiving IP until 12 months if the Investigator judges that they are gaining clinical benefit.

All patients will receive efficacy scans and follow-up care in accordance with standard local clinical practice. Data should be recorded on patient charts but will not otherwise be reported for the purposes of this study.

For patients who are continuing to receive treatment with durvalumab following the final DCO and database closure, it is recommended that the patients continue the scheduled site visits and Investigators monitor the patients' safety laboratory results prior to and periodically during treatment with durvalumab in order to manage AEs in accordance with the durvalumab Dosing Modification and Toxicity Management Guidelines (see Section 8.4.5.1).

Following the DCO, SAE reporting applies only to patients who are active on IP and within 90 days after the last dose; in all other cases, only a Statement of Death notification is to be sent to AstraZeneca. No OS data will be recorded in the study database after DCO for the study.

Investigators will report SAEs to AstraZeneca Patient Safety via paper case report forms (CRFs) until 90 days after the last dose of study drug, in accordance with Section 8.4.1. Any SAE or nonserious AE ongoing at the time of the DCO is to be followed up at the discretion of the Investigator and per local practice and in alignment with the Dosing Modification and Toxicity Management Guidelines (see Section 8.4.5.1), unless the event is considered by the Investigator to be unlikely to resolve, or the patient is lost to follow-up. Data will not be captured for the purposes of this study outside of being recorded in the patients' source documents.

Different drug supply options will be available depending on the country, and these will be proposed to the patient when the most appropriate alternatives for continued treatment have been agreed between AZ and the Investigator. Options may include the participation in a new rollover study or, if the study drug has been locally approved for use in this disease indication, patients may be discontinued and switched to the marketed product, in accordance with local laws. In the event that a rollover or safety extension study is available at the time of the final DCO and database closure, patients currently receiving treatment with durvalumab may be transitioned to such a study, and the current study would reach its end. The rollover or safety extension study would ensure treatment continuation with visit assessments per its protocol. Any patient who would be proposed to move to such a study would be given a new ICF.

Continued Access to Study treatment

As described in Section 4.4, the study will remain open until all patients have discontinued study treatment and completed their last expected visit/contact.

Before the study reaches the final DCO, AstraZeneca will continue to supply durvalumab to patients who were enrolled to receive durvalumab until completion of a patient's current 12-month treatment period or until meeting any other discontinuation criteria, as defined in Section 7.1. Patients should be followed according to the institution's standard of care

assessments. No further data collection is required, except for reporting of AEs and SAEs, however drug dispensation data may be collected in electronic data capture (EDC).

AstraZeneca can continue to supply durvalumab in the continued access phase of this study and after completion of the 12-month treatment period while, in the opinion of the Investigator, the patient is benefiting from durvalumab therapy.

In the event that product development reaches a point where alternative product supply options become available, then these alternative product supply options will be discussed by AstraZeneca with the Investigator. AstraZeneca will work with the Investigator to transition the patient(s) to alternative supply, where possible.

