Patients will be enrolled into 2 cohorts according to radiotherapy pretreatment dose (Cohort A: standard radiation therapy [60 gray (Gy) \pm 10% or hypofractionated bioequivalent dose (BED)]; Cohort B: palliative radiation therapy [40 to < 54 Gy or hypofractionated BED]). This study will be conducted in Europe and North America.

Study period

Estimated date of first patient enrolled: Q2 2020

Estimated date of last patient completed: Q2 2023

Number of patients

Approximately 102 patients are being treated with durvalumab in this study in Europe and North America. Patients will be in complete response (CR), partial response (PR), or have stable disease (SD) following radiation therapy, as assessed by the Investigator and further supported by the screening imaging radiological assessment. Patients must not have progressed following

radiation therapy, and radiation therapy must be completed within 6 weeks (42 days) prior to first durvalumab administration. The last dose of radiation therapy is defined as the day of the last radiation treatment session.

Approximately 148 patients are screened to achieve 102 patients treated with durvalumab and 60 evaluable patients.

Note: "Screened" means a patient's or their legally acceptable representative's, agreement to participate in a clinical study following completion of the informed consent process. Potential patients who are screened for the purpose of determining eligibility for the study, but are not randomized/assigned in the study, are considered "screen failures", unless otherwise specified by the protocol.

Treatments and treatment duration

All patients will receive 1500 mg durvalumab via intravenous (IV) infusion every 4 weeks (q4w) for 12 months (13 doses/cycles). The last administration of durvalumab will be on week 48 unless there is clinical progression, confirmed radiological progression, unacceptable toxicity, withdrawal of consent, or another discontinuation criterion is met. (Please note: If a patient's weight falls to 30 kg or below, the patient should receive weight-based dosing equivalent to 20 mg/kg of durvalumab q4w after consultation between Investigator and Study Physician, until the weight improves to > 30 kg, at which point the patient should resume the fixed-dosing of durvalumab 1500 mg q4w).

Progression during treatment

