5.1 Inclusion criteria

Patients are eligible to be included in the study only if all of the following inclusion criteria and none of the exclusion criteria apply:

Informed consent

- 1 Capable of giving signed informed consent which includes compliance with the requirements and restrictions listed in the informed consent form (ICF) and in this protocol.
- 2 Provision of signed and dated, written ICF prior to any mandatory study specific procedures, sampling, and analyses.
- 3 Provision of signed and dated written genetic ICF prior to collection of sample for genetic analysis (optional).

The ICF process is described in Appendix A 3.

Age

- 4 Age \geq 18 years at the time of screening.

Type of patient and disease characteristics

- 5 Histologically- or cytologically-documented NSCLC with locally-advanced, unresectable Stage III disease (according to the IASLC Staging Manual Version 8 [IASLC 2016]).
 - (a) Imaging to rule out distant metastasis is required.

(b) Endobronchial ultrasound with biopsy is encouraged in patients with suspected lymph node involvement.

6 Deemed ineligible for chemotherapy per Investigator assessment (eg, comorbidities, poor PS, etc).

7 Receipt of radiation therapy that was completed within 42 days prior to first IP dose administration in the study.

8 Patients must have received a total dose of radiation of 40 to 66 Gy (standard or hypofractionated BED). Note that patients will be assigned to Cohort A (standard radiation therapy [60 Gy \pm 10% or hypofractionated BED]) or Cohort B (palliative radiation therapy [40 to < 54 Gy or hypofractionated BED]) based upon total dose of radiation received. Sites are encouraged to adhere to mean organ radiation dosing as follows:

- (a) Mean lung dose < 20 Gy and/or V20 < 35%;
- (b) Mean esophagus dose < 34 Gy;
- (c) Heart V45 < 35% or V30 < 30%. Heart V45 < 35% or V30 < 30%.

Note: Sites should be aware of the recent RTOG 0617 Study data ([Bradley et al 2015](#)) demonstrating that doses higher than 60 Gy may be associated with greater toxicity and worse efficacy.

- (d) Patients with WHO/ECOG PS 2 or chronic lung disease (pulmonary emphysema or chronic obstructive pulmonary disease) must have received a V20 < 25%.

9 Patients must not have progressed following radiation therapy, as per Investigator assessed RECIST 1.1 criteria.

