5.2 Exclusion criteria

Medical conditions

- 1 Patients with locally-advanced NSCLC whose disease has progressed following radiation therapy.
- 2 Mixed small cell lung cancer and NSCLC histology.
- 3 History of allogeneic organ transplantation.
- 4 Active or prior documented autoimmune or inflammatory disorders (including inflammatory bowel disease [eg, colitis or Crohn's disease], diverticulitis [with the exception of diverticulosis], systemic lupus erythematosus, Sarcoidosis syndrome, or Wegener syndrome [granulomatosis with polyangiitis, Graves' disease, rheumatoid arthritis, hypophysitis, uveitis, etc]). The following are exceptions to this criterion:
 - Patients with vitiligo or alopecia
 - Patients with hypothyroidism (eg, following Hashimoto syndrome) stable on hormone replacement
 - Any chronic skin condition that does not require systemic therapy
 - Patients without active disease in the last 5 years may be included but only after consultation with the Study Physician
 - Patients with celiac disease controlled by diet alone
- 5 Uncontrolled intercurrent illness, including but not limited to, ongoing or active infection, symptomatic congestive heart failure, uncontrolled hypertension, unstable angina pectoris,

uncontrolled cardiac arrhythmia, active ILD, serious chronic gastrointestinal conditions associated with diarrhea, or psychiatric illness/social situations that would limit compliance with study requirement, substantially increase risk of incurring AEs or compromise the ability of the patient to give written informed consent

6 History of another primary malignancy except for

- Malignancy treated with curative intent and with no known active disease \geq 5 years before the first dose of durvalumab and of low potential risk for recurrence
- Adequately treated nonmelanoma skin cancer or lentigo maligna without evidence of disease
- Adequately treated carcinoma in situ without evidence of disease

7 History of leptomeningeal carcinomatosis

8 History of active primary immunodeficiency

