7 DISCONTINUATION OF TREATMENT AND PATIENT WITHDRAWAL

7.1 Discontinuation of study treatment

An individual patient will not receive any further treatment (durvalumab) if any of the following occur in the patient in question:

- Withdrawal of consent from further treatment with IP. The patient is, at any time, free to discontinue treatment, without prejudice to further treatment. A patient who discontinues treatment is normally expected to continue to participate in the study (eg, for safety and survival follow-up) unless they specifically withdraw their consent to all further participation in any study procedures and assessments (see Section [7.3](#)).
- An AE that, in the opinion of the Investigator or AstraZeneca, contraindicates further dosing
- Any AE that meets criteria for discontinuation as defined in the Dosing Modification and Toxicity Management Guidelines (see Section [8.4.5.1](#))
- Pregnancy or intent to become pregnant
- Noncompliance with the study protocol that, in the opinion of the Investigator or AstraZeneca, warrants withdrawal from treatment with IP (eg, refusal to adhere to scheduled visits)
- Initiation of alternative anticancer therapy including another investigational agent
- Clinical progression or confirmed radiological progression (refer to [Appendix F](#)) and Investigator determination that the patient is no longer benefiting from treatment with IP.

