  - Intranasal, inhaled, topical steroids, or local steroid injections (eg, intra articular injection)
  - Systemic corticosteroids at physiologic doses not to exceed 10 mg/day of prednisone or its equivalent
  - Steroids as premedication for hypersensitivity reactions (eg, CT scan premedication)
- Deviation 2: The patient met discontinuation criteria but did not discontinue durvalumab (eg, patient withdrew consent, patient became pregnant).
- Deviation 3: The patient received a prohibited concomitant medication or procedure as detailed in Section 6.4 of the CSP or any other concomitant medication or procedure which, upon physician review of all medications and procedures prior to database lock (DBL), is considered to have a potential effect on study outcomes.
- Deviation 4: Missed visits, assessments, or treatments that, in the opinion of the principal investigator,
  - were due to the 2020 COVID-19 global pandemic and
  - there was a significant effect on either completeness, accuracy, and/or reliability of the patient's data, or the patient's rights, safety or well-being.

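### The progression stopping criterion is worded differently across sections, the exempted-criteria list in Protocol 6.1.3 omits exclusion criterion 1, and SAP Deviation 2 does not say which rule it counts against

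*Protocol*

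**What the plan says.** **The stop.** The Synopsis has treatment run to week 48 "unless there is clinical progression, confirmed radiological progression, unacceptable toxicity" or another stopping reason applies. Protocol 6.1.2.1 has an almost identical sentence with a different trigger: "unless there is clinical progression, RECIST 1.1-defined radiological progression, unacceptable toxicity". The opening of 6.1.3 and SAP 1.2.1 follow the 6.1.2.1 version. Protocol 4.1 names RECIST 1.1 progression by the Investigator. Protocol 4.2.4 requires RECIST progression together with the Investigator's finding that the patient no longer benefits. Protocol 7.1 lists "Clinical progression or confirmed radiological progression", and the same bullet adds the Investigator's finding of no further benefit.

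**Continuing after progression.** The Synopsis (progression during treatment) and 6.1.3 let clinically stable patients continue after a first RECIST progression. Both also let patients with confirmed progression continue, after consultation with the sponsor, for what is left of the 12 months. Appendix F (Confirmation of Radiological Progression) instead lets such patients continue until clinical benefit ends. Section 6.1.3 bars continuation when target lesions progress after a confirmed response in those lesions; 7.1 does not list this bar.

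**The condition.** Under 6.1.3 the patient must still meet the eligibility criteria, "with the exception of inclusion criteria 9, 11, and 14 and exclusion criterion 17". Inclusion 9 reads "Patients must not have progressed following radiation therapy, as per Investigator assessed RECIST 1.1 criteria". Exclusion 1 reads "Patients with locally-advanced NSCLC whose disease has progressed following radiation therapy".

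**The deviation.** SAP 2.2.1 makes this an important deviation: "The patient met discontinuation criteria but did not discontinue durvalumab". It gives withdrawn consent and pregnancy as examples and cites no section. SAP 4.2.2 reports number and percentage for each deviation category.

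**The concern.** Two sites holding the same protocol could stop the same patient at different points, each able to cite a section in support. The paragraph that governs who may stay on durvalumab after progression also contains a condition that, taken at its word, no patient with progression can meet.

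For the analysis, the consequence is that Deviation 2 has no single reference rule. A programmer working from SAP 1.2.1 and one working from Protocol 7.1 would flag different patients from the same data. Exposure accumulated after progression would also reflect which section a site happened to follow.

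**Working it through.** The plan gives no figure here, so the check is on the text.

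**Exemption list.**
1. Every treated patient has had radiotherapy, by inclusion 7: "Receipt of radiation therapy that was completed within 42 days prior to first IP dose administration in the study".
2. Any progression on study is therefore progression after radiotherapy, which is what exclusion 1 describes.
3. The list in 6.1.3 exempts inclusion 9, which has the same content, but not exclusion 1.
4. SAP 2.2.1 lists inclusion 9 and exclusion 1 as separate key criteria, so exempting one does not formally exempt the other. Protocol section 5 allows no waivers of entry criteria.
5. Read literally, a patient with progression fails the condition for continuing, although the same section permits continuation.

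**Deviation 2 count.** Take six invented patients, all kept on durvalumab (assumptions, not trial data):
- A: first RECIST progression, not confirmed, benefiting
- B: confirmed progression, benefiting
- C: confirmed progression, not benefiting
- D: confirmed progression in target lesions after a target-lesion response, benefiting
- E: clinical progression only, benefiting
- F: clinical progression only, not benefiting

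Applying each stop sentence on its own:

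| Rule used | Patients counted | Count |
|---|---|---|
| Protocol 4.1 | A, B, C, D | 4 of 6 |
| Protocol 4.2.4 | C | 1 of 6 |
| Protocol 6.1.2.1, SAP 1.2.1 | A to F | 6 of 6 |
| Synopsis stop sentence | B, C, D, E, F | 5 of 6 |
| Protocol 7.1, no-benefit condition applied to both kinds of progression | C, F | 2 of 6 |
| Protocol 7.1, no-benefit condition applied to confirmed progression only | C, E, F | 3 of 6 |
| Protocol 6.1.3 read literally | A to F | 6 of 6 |

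The range is 1 to 6 for the same patients. Section 7.1 alone gives 2 or 3, because its bullet can be parsed two ways. If 6.1.3 is read as though exclusion 1 were also exempt (an illustration, not a proposal), it counts C, D, E and F, 4 of 6. Resolving the list alone would therefore not settle the count.

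**Timing.** Section 6.1.3 places the follow-up scan 4 to 8 weeks after progression, which is 4/4 = 1 to 8/4 = 2 cycles. The Synopsis and Appendix F place it no later than the next scheduled scan and at least 4 weeks on; scheduled scans are 8 weeks apart to week 48 and 12 weeks apart after that. Confirmed progression need not end treatment under the Synopsis, 6.1.3, 7.1 or Appendix F. The scan interval is therefore not the difference in treatment time between the rules.

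**What the choice of section does not touch.** SAP 2.1.1 puts every dosed patient in the safety analysis set. SAP 3.3.1 counts progression for PFS whether or not durvalumab continues. The 90-day AE period (Protocol 8.3.2, SAP 3.2.3) and the exposure formulas (SAP 3.2.8) run from actual dose dates.

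**The case against.** **General rule and exception.** Sections 4.1 and 6.1.2.1 can be read as the default stop, with 6.1.3 as the stated exception; 4.1 refers the reader to 6.1.3 for detail. Different stopping points for different patients are then partly intended discretion. This stands in part. It does not explain why two near-identical sentences in the Synopsis and 6.1.2.1 name different triggers, or why Appendix F and 6.1.3 end treatment after confirmed progression at different points.

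**The exemption list.** A reader might infer that nobody can continue after progression. The documents do not support that as the intended rule: 6.1.3 expressly permits continuation and exempts inclusion 9, so leaving out exclusion 1 looks like a drafting slip. It could also be argued that exclusion 1 concerns only progression before entry. But inclusion 9 is worded the same way and was exempted, which would have been unnecessary if such wording applied at entry only.

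**Deviation 2.** A reader might infer that the count is undefined. That goes too far. Section 4.2.4, the footnote to Figure 2 and the continued-access text in 6.1.3 all point to 7.1 for discontinuation criteria, and both SAP examples match bullets there. SAP 2.2.2 also has classifications reviewed and finalised before database lock or data cut-off. Section 7.1 is the likely source. Even so, SAP 1.2.1 words the trigger differently, 7.1 omits the bar after a target-lesion response, and its progression bullet is ambiguous. A review meeting needs a rule to apply.

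**Conclusion.** The inconsistency is real and should be corrected, but its reach is limited. The progression stop is worded five ways, the exemption list in 6.1.3 works against the permission it accompanies, and the Deviation 2 count is not uniquely defined. The 1-to-6 range rests on six invented profiles; it shows that the count depends on the section and does not predict the trial's count.

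The effect is on dosing and exposure after progression and on one row of the important-deviation table. Three stronger inferences are not supported:
- **A fixed treatment gap of 8 weeks, or two cycles, per patient with progression.** Confirmed progression does not necessarily end treatment, and the follow-up scan has no fixed interval.
- **Deviation 2 flagging either all or none of those treated past first progression.** The stop sentences give intermediate counts, and none of them gives zero.
- **A change in the AE window or the analysis populations.** The window's end follows the actual last dose, and its derivation is the same whichever section a site used. The safety analysis set and the PFS definition do not depend on the stopping rule.

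**What to change.** 1. Reconcile the progression wording to one criterion in the Synopsis (treatment duration and progression during treatment), Protocol 4.1, 4.2.4, 6.1.2.1, 6.1.3 (including the bar after a target-lesion response), 7.1, Appendix F and SAP 1.2.1. This includes the differing end points for treatment after confirmed progression and the two possible readings of the 7.1 bullet.
2. Make the exempted-criteria list in 6.1.3 consistent with exclusion criterion 1.
3. Have SAP Deviation 2 cite the section that governs discontinuation.

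Which clinical rule applies is for the sponsor to decide; this review takes no position. The cost is a protocol text amendment, a wording change in SAP 1.2.1 and one cross-reference in SAP 2.2.1. No analysis set or endpoint definition needs to change.
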